2.1.1 General definitions

Investigational drug and study treatment

Investigational drug, will refer to either ruxolitinib (INC424) or any of the novel agents. Whereas, **study treatment** will refer to ruxolitinib single agent or in combination with any of the novel agents.

Date of first administration of investigational drug

The date of first administration of investigational drug is defined as the first date when a nonzero dose of investigational drug is administered and recorded on the Dosage Administration Record (DAR) (e)CRF. The date of first administration of study drug will also be referred as start of investigational drug.

Date of last administration of investigational drug

The date of last administration of investigational drug is defined as is the last date when a nonzero dose of investigational drug is administered and recorded on DAR eCRF. The date of last administration of investigational drug will also be referred as end of investigational drug.

Date of first administration of study treatment

The date of first administration of study treatment is derived as the first date when a nonzero dose of study treatment was administered as per the Dosage Administration CRF. The date of first administration of study treatment will also be referred as *start of study treatment*.

Date of first administration of extension phase study treatment

The date of first administration of extension phase study treatment is derived as the first date when a nonzero dose of extension phase study treatment was administered as per the Dosage Administration CRF for subject who entered extension treatment phase.

Date of last administration of study treatment

The date of last administration of study treatment is defined as the last date when a nonzero dose of study treatment was administered as per Dose Administration (e)CRF.

Study day

The study day describes the day of the event or assessment date, relative to the reference start date.

The study day is defined as:

- The date of the event (visit date, onset date of an event, assessment date etc.) – reference start date + 1 if event is on or after the reference start date;
- The date of the event (visit date, onset date of an event, assessment date etc.) – reference start date if event precedes the reference start date.

The reference date for all assessments (safety, efficacy, PK, QoL, etc.) is the start of study treatment.

The study day will be displayed in the data listings. If an event starts before the reference start date, the study day displayed on the listing will be negative.

Time unit

A year length is defined as 365.25 days. A month length is 30.4375 days (365.25/12). If duration is reported in months, duration in days will be divided by 30.4375. If duration is reported in years, duration in days will be divided by 365.25.

Baseline

For safety and efficacy evaluations, the last available assessment on or before the date of start of study treatment is defined as “baseline” assessment.

In case time of assessment and time of treatment start is captured (e.g. pre-dose ECG), the last available assessment before the treatment start date/time is used for baseline.

For safety parameters (e.g ECGs or vital signs), where study requires multiple replicates per time point, the average of these measurements would be calculated for baseline (if not already available in the database).

If patients have no value as defined above, the baseline result will be missing.

On-treatment assessment/event and observation periods

The overall observation period will be divided into three mutually exclusive segments:

1. ***pre-treatment period***: from day of subject's informed consent to the day before first administration of study treatment
2. ***on-treatment period***: from date of first administration of study treatment to 30 days after date of last actual administration of any study treatment (including start and stop date)
3. ***post-treatment period***: starting at day 31 after last administration of study treatment.

Moreover, ***on-extension treatment period*** is defined from day of first administration of extension phase study treatment to 30 days after the date of the last administration of study treatment.

In addition, the ***overall safety period*** is defined for this study as following:

Overall safety period: from date of first administration of study treatment to 30 days after the date of the last administration of ruxolitinib, siremadlin or rineterkib, 90 days after the date of the last administration of NIS793, or 105 days after the date of the last administration of crizanlizumab, or 150 days after the date of the last administration of sabatolimab, whichever is later.

Safety summaries (tables, figures) include data from the pre-treatment period (to display the baseline status e.g. for ECG) and the on-treatment period, i.e. data from the post-treatment period with the exception of deaths should not be included unless requested from Health Authorities or external committees.

In particular, summary tables for adverse events (AEs) will summarize on-treatment events, with a start date during the on-treatment period, the so-called ***treatment-emergent*** AEs. Additionally, all (study treatment related/ regardless) AEs and SAEs with a start date during the overall safety period will be summarized.

However, all safety data (including those from the post-treatment period) will be listed and those collected during the pre-treatment, post-treatment overall safety period and post-treatment period are to be flagged.

For the final analysis, all extension treatment phase safety data will be listed and those collected during post-treatment overall safety period and post-treatment period are to be flagged. The safety data in part 1 core and extension phase will be summarized in tables for the extension treatment phase clinical trial safety disclosure.

Windows for multiple assessments

In order to summarize data collected over time (including unscheduled visits), the assessments will be time slotted. The following general rule will be applied in creating the assessment windows: If more than one assessment is done within the same time window, the assessment performed closest to the target date will be used. If two assessments within a time window are equidistant from the target date, then the assessment that occurred later will be used. If multiple assessments occur on the same date then the worst case will be used. Data from all assessments (scheduled and unscheduled), including multiple assessments, will be listed.

The following time windows are defined for descriptive summary on spleen imaging, spleen length palpation, ePROs, laboratory assessments [REDACTED] (Tables 2-1, 2-2, and 2-3) by visit regardless of core or extension treatment phases. The end of treatment assessment will be mapped into the time points as needed.

Table 2-1 Time windows for imaging assessments (MRI/CT of abdomen)

Time Point	Planned Visit Timing	Time Window Definition
Screening/Baseline	On or before Study Day 1*	≤ Study Day 1
Cycle 7 Day 1	Study Day 168	Study Days 140 – 196
Cycle 13 Day 1	Study Day 336	Study Days 308 – 364
Every 6 cycles thereafter		
Cycle $y=13+6*k$ Day 1 (with $k = 1, 2, \dots$)	Study Day $(13+6*k-1)*28$	Study Days $(13+6*k-1)*28-28$ to $(13+6*k-1)*28+28$

* Study Day 1 = Date of first administration of study treatment (start of study treatment)

EOT core and EOT extension assessments are mapped to the corresponding time points based on the defined time window.

Table 2-2 Time windows for ePROs, laboratory assessments (chemistry, coagulation, urinalysis and thyroid function) [REDACTED]

Time Point	Planned Visit Timing	Time Window Definition
Baseline (Cycle 1 Day 1)	On or before Study Day 1*	≤ Study Day 1
Cycle 2 Day 1	Study Day 29	Study Days 15 – 42
Cycle 3 Day 1	Study Day 57	Study Days 43 – 70
Cycle 4 Day 1	Study Day 85	Study Days 71 – 98

Cycle 5 Day 1	Study Day 113	Study Days 99 – 126
Cycle 6 Day 1	Study Day 141	Study Days 127 – 154
Cycle 6+k Day 1 (with k = 1, 2, ...)	Study Day (6+k-1)*28+1	Study Day (6+k-1)*28+1-14 to (6+k-1)*28+14
Post treatment		
30-day safety follow-up	Post treatment study day 30	Post treatment study days 23 – 37
90-day safety follow-up	Post treatment study day 90	Post treatment study days 83 – 97
105-day safety follow-up	Post treatment study day 105	Post treatment study days 98 – 112
150-day safety follow-up	Post treatment study day 150	Post treatment study days 136 – 164

* Study Day 1 = Date of first administration of study treatment (start of study treatment)
 EOT core and EOT extension assessments are mapped to the corresponding time points based on the defined time window.
 Post treatment study day 1 = end of study treatment date + 1
 Post treatment visits are for laboratory chemistry assessments only
 90-day safety follow-up visit for NIS7393 arm(s)
 90-day safety follow-up visit, and 150-day safety follow up visit are for sabatolimab arm(s)
 105-day safety follow-up visit is for crizanlizumab arm(s)

Table 2-3 Time windows for spleen length palpation assessments and hematology laboratory assessments

Time Point	Planned Visit Timing	Time Window Definition
Baseline (Cycle 1 Day 1)	On or before Study Day 1*	≤ Study Day 1
Cycle 1 Day 15	Study Day 15	Study Days 8 – 21
Cycle 2 Day 1	Study Day 29	Study Days 22 – 35
Cycle 2 Day 15	Study Day 43	Study Days 36 – 49
Cycle 3 Day 1	Study Day 57	Study Days 50 – 63
Cycle 3 Day 15	Study Day 71	Study Days 64 – 77
Cycle 4 Day 1	Study Day 85	Study Days 78 – 98
Cycle 5 Day 1	Study Day 113	Study Days 99 – 126
Cycle 6 Day 1	Study Day 141	Study Days 127 – 154
Cycle 6+k Day 1 (with k = 1, 2, ...)	Study Day (6+k-1)*28+1	Study Day (6+k-1)*28+1-14 to (6+k-1)*28+14
Post treatment		
30-day safety follow-up	Post treatment study day 30	Post treatment study days 23 – 37
90-day safety follow-up	Post treatment study day 90	Post treatment study days 83 – 97
105-day safety follow-up	Post treatment study day 105	Post treatment study days 98 – 112
150-day safety follow-up	Post treatment study day 150	Post treatment study days 136 – 164

* Study Day 1 = Date of first administration of study treatment (start of study treatment)
EOT core and EOT extension assessments are mapped to the corresponding time points based on the defined time window.
Post treatment study day 1 = end of study treatment date + 1
Post treatment visits are for laboratory hematology assessments only
90-day safety follow-up visit for NIS7393 arm(s)
90-day safety follow-up visit, and 150-day safety follow up visit are for sabatolimab arm(s)
105-day safety follow-up visit is for crizanlizumab arm(s)

Last contact date

The last contact date will be derived for patients not known to have died at the analysis cut-off using the last complete date among the following:

Source data	Conditions
Date of Randomization	No Condition
Last date patient was known to be alive from Survival Follow-up page	Patient status is reported to be alive, lost to follow-up or unknown.
Start/End dates from further antineoplastic therapy	Non-missing medication/procedure term.
Start/End* dates from drug administration record	Non-missing dose. Doses of 0 are allowed.
End of treatment date from end of treatment page	No condition.
Efficacy assessment date if available (e.g., spleen imaging/palpation assessment, bone marrow assessment, ePRO assessment)	Evaluation is marked as 'done'.
Laboratory/PK collection dates/ [REDACTED] [REDACTED]	Sample collection marked as 'done'.
Vital signs date	At least one non-missing parameter value
Performance Status date	Non-missing performance status
Start/End dates of AE	Non-missing verbatim term

The last contact date is defined as the latest complete date from the above list or the cut-off date whichever comes first. The cut-off date will not be used for last contact date, unless the subject was seen or contacted on that date. No date post cut-off date will be used. Completely imputed dates (e.g. the analysis cut-off date programmatically imputed to replace the missing end date of a dose administration record) will not be used to derive the last contact date. Partial date imputation is allowed for event (death)/censoring is coming from 'Survival information' eCRF.

The last contact date will be used for censoring of patients in the analysis of survival analysis.

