If the event worsens the event should be reported a second time in the CRF noting the start date when the event worsens in toxicity. For grade 3 and 4 adverse events only, if improvement to a lower grade is determined a new entry for this event should be reported in the CRF noting the start date when the event improved from having been Grade 3 or Grade 4.

Conditions that were already present at the time of informed consent should be recorded in medical history of the subject.

Adverse events (including lab abnormalities that constitute AEs) should be described using a diagnosis whenever possible, rather than individual underlying signs and symptoms.

Adverse event monitoring should be continued for at least:

- 30 days after the last dose of single-agent ruxolitinib (control/monotherapy)
- 30 days after the last dose of ruxolitinib or siremadlin for subjects on ruxolitinib + siremadlin (or siremadlin monotherapy in Part 3)
- 30 days after the last dose of ruxolitinib or rineterkib for subjects on ruxolitinib + rineterkib (or rineterkib monotherapy in Part 3)
- 90 days after the last dose of NIS793 for subjects on ruxolitinib + NIS793 (or NIS793 monotherapy in Part 3)
- 105 days after the last dose of crizanlizumab for subjects on ruxolitinib + crizanlizumab (or crizanlizumab monotherapy in Part 3)
- 150 days after the last dose of sabatolimab for subjects on ruxolitinib + sabatolimab (or sabatolimab monotherapy in Part 3).

OR

until the start of a new post treatment anti-neoplastic medication if sooner than the end of the safety follow-up period mentioned above, depending on the study treatment. If a subject starts post treatment antineoplastic medication, then only adverse events suspected to be related to study treatment should be collected, up to the end of the safety follow-up period noted above.

Progression of the underlying disease (myelofibrosis) (including fatal outcomes) based on the criteria described in Section 8.3.2.3 (ie. progressive splenomegaly, increase in peripheral blood blast content of > 10% (accelerated phase), deteriorating cytopenia, leukemic transformation) should not be reported as a serious adverse event. These disease progression events will be reported on specific CRF pages other than the AE CRF.

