
• To characterize the pharmacokinetic profile of ruxolitinib administered in combination with sitemartin, crizanlizumab, sabatolimab, rinaterkib and NIS793, respectively (Part 1 core)• To assess emergence of anti-crizanlizumab, anti-sabatolimab, or anti-NIS793 antibodies following one or more IV infusions (Part 1 core)• To evaluate the changes in spleen size in each treatment arm (Part 1 core and extension)• To evaluate long-term safety and tolerability of ruxolitinib combination treatments in each arm (Part 1 core and extension)	
• Cycle 16 (NIS793 arms) or Cycle 12 (all other arms) from baseline.• PK parameters (e.g., AUC, Cmax, Tmax) and concentration vs. time profiles of each investigational drug with in combination regimens• Presence and/or concentration of anti-crizanlizumab, anti-sabatolimab or anti-NIS793 antibodies• Change in spleen length (by palpation) from baseline.• Change in spleen volume (by MRI/CT) from baseline, including proportions of subjects who achieved (i) at least 35% spleen volume reduction and (ii) at least 25% spleen volume reduction at the end of Cycle 8 (NIS793 arms) or Cycle 6 (all other arms, and at the end of Cycle 16 (NIS793 arms) or Cycle 12 (all other arms), or Cycle 21 (extension phase) from baseline respectively.• Frequency, duration and severity of adverse events, abnormalities in vital signs and laboratory test values, including ECG data

2 Statistical methods

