2.8.1 Adverse events (AEs)

AE summaries will include all AEs occurring (new or worsening) during the **on treatment period**. In addition, all AEs and SAEs which started during the **overall safety period** will be summarized. AEs collected in the AE (e)CRF page will be listed along with the information collected on those AEs e.g. AE relationship to study drug, AE outcome etc. AEs with start date outside of on-treatment period (pre-treatment period, post-treatment period, and post-treatment overall safety period) will be flagged in the listings.

AEs will be summarized by number and percentage of subjects having at least one AE, having at least one AE in each primary system organ class (SOC) and for each preferred term (PT) using MedDRA coding. A subject with multiple occurrences of an AE will be counted only once in the respective AE category. Grading of AEs is based on NCI Common Terminology Criteria for Adverse Events (CTCAE) version 5.0. A subject with multiple CTCAE grades for the same preferred term will be summarized under the maximum CTCAE grade recorded for the event . AE with missing CTCAE grade will be included in the 'All grades' column of the summary tables.

In AE summaries, the primary system organ class will be presented alphabetically and the preferred terms will be sorted within primary SOC in descending frequency. The sort order for the preferred term will be based on their frequency in the total column.

The following adverse event summaries will be produced by treatment arm; overview of adverse events and deaths (number and % of subjects who died, with any AE, any SAE, any dose reductions/interruptions, leading to treatment discontinuation, requiring additional therapy), AEs by SOC and PT, summarized by relationship (all AEs and AEs related to study treatment), seriousness (SAEs and non-SAEs), leading to treatment discontinuation, leading to dose interruption/adjustment, requiring additional therapy and leading to fatal outcome. In addition, a summary of serious adverse events with number of occurrences will be produced (an occurrence is defined as >1 day between start and prior end date of record of same preferred term).

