2.8.1.2 Adverse events of clinical trial safety disclosure

For the legal requirements of ClinicalTrials.gov and EudraCT, two required tables on adverse events which are not serious adverse events with an incidence greater than 5% and on serious adverse events and SAE suspected to be related to study treatment will be provided by system organ class and preferred term on the safety set population.

If for a same patient, several consecutive AEs (irrespective of study treatment causality, seriousness and severity) occurred with the same SOC and PT:

- a single occurrence will be counted if there is ≤ 1 day gap between the end date of the preceding AE and the start date of the consecutive AE
- more than one occurrence will be counted if there is > 1 day gap between the end date of the preceding AE and the start date of the consecutive AE

For occurrence, the presence of at least one SAE / SAE suspected to be related to study treatment / non SAE has to be checked in a block e.g., among AE's in a ≤ 1 day gap block, if at least one SAE is occurring, then one occurrence is calculated for that SAE.

The number of deaths resulting from SAEs suspected to be related to study treatment and SAEs irrespective of study treatment relationship will be provided by SOC and PT.

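### Treatment-emergent AEs are flagged by record start date alone, so a grade 3/4 event that began in screening and only improved on treatment qualifies, against the plan's own limit to new or worsened events

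*SAP*

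**What the plan says.** **How events are recorded.** Protocol 10.1.1 splits one event into several CRF records. If an event worsens, "the event should be reported a second time in the CRF" with the date of worsening. For grade 3 and 4 events only, improvement also creates a record: "a new entry for this event should be reported in the CRF noting the start date when the event improved". Conditions already present at consent go to medical history, not to the AE page.

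**How treatment-emergent events are selected.** SAP 2.1.1 says "summary tables for adverse events (AEs) will summarize on-treatment events, with a start date during the on-treatment period" and calls these events treatment-emergent. SAP 2.8 repeats the start-date rule, and so does the opening paragraph of Protocol 12.5.2. The overall safety period summaries in SAP 2.1.1 and 2.8.1 are also selected by start date.

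**The limiting text.** SAP 2.8.1 says "AE summaries will include all AEs occurring (new or worsening) during the" on-treatment period. The adverse-event paragraph of Protocol 12.5.2 likewise confines the tables to events that began or got worse on treatment.

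**Linking of records.** SAP 2.8.1.2 has a rule for joining adjacent records of the same term: "a single occurrence will be counted if there is ≤ 1 day gap between the end date of the preceding AE" and the start of the next. It belongs to the public-disclosure tables. SAP 2.8.1 uses a similar one-day definition for the table of SAE occurrences.

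**The concern.** A start-date rule works when a record's start date is the onset of an event or the date it worsened. Here it can also be the date an event improved, and nothing in the start date tells the two apart. A programmer who follows SAP 2.1.1 and 2.8 as written will flag some improving pre-treatment events as treatment-emergent. One who follows SAP 2.8.1 has no stated way to compare a record's grade with the record before first dose.

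The AE tables carry much of what this trial will now report, since only Part 1 objectives are pursued and treatment groups are small. A single misclassified subject is visible as a percentage in a group of about six.

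**Working it through.** The plan gives no figure to reproduce. The check traces the recording rule through each selection rule.

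**Inputs**
- Screening lasts up to 28 days (Protocol 3). The pre-treatment period runs from consent to the day before first dose (SAP 2.1.1).
- An improving grade 3/4 event gets a new record starting on the day of improvement (Protocol 10.1.1).
- Selection is by start date (SAP 2.1.1 and 2.8), or limited to new or worsened events (SAP 2.8.1 and Protocol 12.5.2).
- Group size is about 6 (Protocol 6.1.3).

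**Case 1: improvement.** A constructed subject consents on Day -20. A grade 3 event starts on Day -10 (record 1) and improves to grade 2 on Day 8 (record 2, start Day 8).
- Start-date rule: record 1 is pre-treatment and record 2 is treatment-emergent. Count = 1, from a grade 2 record.
- New-or-worsened rule: record 2 is neither. Count = 0.

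**Case 2: worsening.** A grade 2 event starts on Day -10 and becomes grade 3 on Day 8 (record 2, start Day 8). Both rules give count = 1, correctly. Record 2 has the same start date as in Case 1, so the start date alone cannot separate the two cases.

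**Case 3: present before consent.** The condition is medical history and has no AE record. Count = 0 under both rules.

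**Does another rule settle Case 1?**
- The maximum-grade rule in SAP 2.8.1 chooses the grade under which a subject appears. It does not decide whether the event is treatment-emergent.
- Counting each subject once per term does not help, because record 2 is the only on-treatment record and is enough to count the subject.
- The one-day-gap rule governs occurrence counts in the disclosure and SAE tables, not the treatment-emergent flag.

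**Size of one miscount.** 1/6 = 16.7%, or about 17 percentage points for that preferred term, if the subject has no other on-treatment record of it. How many subjects are in Case 1 cannot be worked out from either document.

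**The case against.** The strongest reply is that the AE section proper, SAP 2.8.1, already excludes a record opened because a grade fell, as does Protocol 12.5.2. On that reading SAP 2.1.1 and 2.8 are only looser statements of the same rule. This stands in part: it shows what the authors meant, and a miscount is not certain. But Protocol 12.5.2 contains both forms of the rule, the start-date form appears twice in the SAP, and no derivation is given for the narrower form.

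The scope objection stands in full. Only grade 3/4 events that start after consent and before first dose, and improve on treatment, are affected. Entry limits on neutrophils, platelets, liver enzymes and QTcF (Protocol 5.1 and 5.2) remove many candidates. Anemia will usually be pre-existing, because hemoglobin below 11 g/dL is an inclusion criterion.

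It is also true that all AEs are listed with pre-treatment starts flagged, so both records can be seen in a small group. That helps a reader find the problem but does not correct the table.

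A reader might go further and infer that record splitting shortens the reported duration of severe events, since the endpoint includes "Frequency, duration and severity of adverse events". The documents do not support that as a finding. The summaries listed in SAP 2.8.1 include no AE duration table and no per-record duration, so there is no planned output to be biased. Subject-level tables of events arising on treatment are not distorted by splitting either, because each subject is counted once at the maximum grade.

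**Conclusion.** The plan contains an internal inconsistency with no rule to resolve it. The start-date definition, taken literally, gives a count that the plan's own limiting text says should not be made: one subject instead of none in the constructed case. It is tempting to say that improving pre-treatment events will be counted as treatment-emergent. The documents support only that they are counted if SAP 2.1.1 and 2.8 are programmed as written.

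The effect is about 17 percentage points per affected subject for one preferred term in a group of six, assuming no other on-treatment record of that term. No projection of how many subjects are affected is justified, because neither document gives the frequency of such events. The DLT endpoint has its own definition in Protocol 6.5.3 and does not depend on this flag. This is a small defect, worth correcting because the correction is simple.

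**What to change.** In SAP 2.1.1 and 2.8, add that:
- a record opened only because the grade improved is not treatment-emergent;
- an event is treatment-emergent if its first onset is on or after first dose, or if its grade rises above the last pre-dose grade on or after first dose;
- to set this flag, and for no other purpose, records of the same subject and preferred term with a gap of one day or less are linked, including across first dose, using the rule already written in SAP 2.8.1.2.

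Apply the same rule to the overall safety period summaries. Improvement-only records stay in the listings.

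Confining the linkage to the flag avoids rebuilding the other AE tables on episodes, and avoids merging adjacent but separate events where causality or seriousness is reported. The cost is a few sentences in the SAP and a small change to one derived flag, to be made before the final database lock. No new data collection is needed.
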